1.3 Investigation Administration

This investigation will be conducted in accordance with global regulations including ICH GCP, ISO 14155, and 21 CFR 812.

1.4 Investigator

Contact information and qualifications of the co-global principal investigators, principal clinical investigators, clinical investigators, and core laboratories will be maintained by the data coordinating center.

1.5 Monitoring Arrangements

The conduct of the clinical study will be supervised through a process of centralized and on-site monitoring. The data coordinating center will remotely monitor the study for data completeness and for adverse events. On-site monitoring will be implemented as necessary throughout the course of the study. The investigator/institution will provide direct access to source data/documents for study-related monitoring, audits, IRB/EC review and regulatory inspection. Written procedures for monitoring the study are maintained by the data coordinating center and are summarized in Appendix A.

2.0 Approval and Agreement of the Clinical Investigation Plan

The sponsor, co-global principal investigators, and principal clinical investigators for each investigative site will agree to this document and any modifications. Justification for any modifications will be documented. Approval and agreement will be indicated by signing and dating the signature page included in this document.

3.0 Clinical Investigation Plan Overview

The following is a Clinical Investigation Plan to evaluate the safety and effectiveness of the Zilver[®] Vena[™] Venous Stent in the treatment of symptomatic iliofemoral venous outflow obstruction. Patients with symptomatic venous outflow obstruction in one iliofemoral venous segment will be eligible to receive the Zilver[®] Vena[™] Venous Stent. The treated venous segment (i.e., study lesion) will not extend into the inferior vena cava or below the level of the lesser trochanter.

Primary study endpoints will include freedom from major adverse events at 30 days and primary quantitative patency at 12 months. The secondary endpoint will be the change from baseline in the Venous Clinical Severity Score (VCSS) at 1 and at 12 months. [Information redacted due to confidential content.]

This study is designed as a prospective, non-randomized, multi-center study involving up to 40 investigative sites globally. The results of this study will be compared to performance goals derived from the literature. The clinical study intends to enroll 243 patients, and will involve follow-up through 3 years post stent placement. The study flow diagram is presented in Figure 3.1.

[figure not shown]

Figure 3.1. Study flow diagram

^aVDS: Venous Disability Score, ^bCEAP: score of Clinical, Etiological, Anatomic, and Pathophysiologic features,

^cCIVIQ: Chronic Venous Insufficiency Quality of Life Questionnaire, ^dVCSS: Venous Clinical Severity Score

^eBoth obliques of the pelvis recommended.

^fIf patient is symptomatic and ultrasound is inadequate to assess clinical patency, venography will be performed.

4.0 Objectives of the Clinical Investigation

4.1 Objectives

The objectives of this investigation are to evaluate the safety and effectiveness of the Zilver[®] Vena[™] Venous Stent in the treatment of symptomatic iliofemoral venous outflow obstruction.

4.1.1 Primary Safety Endpoint

The primary safety endpoint will be 30-day freedom from major adverse events (MAE), where MAE is defined as procedural bleeding requiring transfusion, procedure- or device-related death, clinically driven target lesion reintervention, clinical migration, new symptomatic pulmonary embolism, or procedure-related perforation requiring open surgical repair or flow-limiting dissection of the target vessel.

4.1.2 Primary Effectiveness Endpoint

The primary effectiveness endpoint will be primary quantitative patency (see Definitions) of the Zilver[®] Vena[™] Venous Stent as assessed by venography at 12-month follow-up.

4.1.3 Secondary Endpoints

The secondary endpoint will be the change from baseline in the VCSS at 1 and at 12 months.

4.1.4 Additional Measures

[Information redacted due to confidential content.]

4.2 Specific Hypotheses to be Accepted or Rejected by Statistical Data

4.2.1 Primary Safety Hypothesis

The primary safety endpoint is 30-day freedom from major adverse events (MAE), and will be analyzed based on the intent-to-treat population. The analysis requires that the performance goal (π_{PGS}) of 87% be met for 30-day freedom from MAE, where π_{PGS} is a weighted average of 85% (computed based on safety data for patients with acute disease, defined as initial symptom onset within 30 days of the procedure) and 88% (computed based on safety data for patients with chronic disease, defined as initial symptom onset greater than 30 days before the procedure), with the weight being prespecified as 30% acute patients and 70% chronic patients. Both 85% and 88% were computed based on 30-day safety data available in the published literature describing patients treated with commercially available stents for acute and chronic iliofemoral venous outflow obstruction, respectively.¹⁻³⁹ The safety of the Zilver[®] Vena[™] Venous Stent will be established provided the null hypothesis is rejected in favor of the alternative hypothesis with the Binomial test for one proportion at the Type I error level of 0.025.

Let π_{S} (where S stands for safety) be the probability that a randomly selected patient is free from a MAE at 30 days, then the hypothesis is formulated as follows:

Null Hypothesis: The 30-day freedom from MAE for patients treated with the Zilver[®] Vena[™] Venous Stent does not meet the performance goal (87%).

$$H_0: \pi_{\text{S}} \leq \pi_{\text{PGS}}; \text{ or } H_0: \pi_{\text{S}} \leq 87\%$$

Alternate Hypothesis: The 30-day freedom from MAE for patients treated with the Zilver[®] Vena[™] Venous Stent meets the performance goal (87%).

$$H_a: \pi_{\text{S}} > \pi_{\text{PGS}}; \text{ or } H_a: \pi_{\text{S}} > 87\%$$

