8.10 Sample Size

Sample size calculations are presented in section 9.1. Based on this analysis, it is estimated that a minimum of 218 patients is required to fulfill enrollment. Cook intends to enroll 243 patients at up to 40 investigative sites to account for those who withdraw or are lost to follow-up.

Consistent with the derivation of the primary safety hypothesis, approximately 30% of the enrolled patient population will have acute disease (defined as initial symptom onset within 30 days of the procedure) and approximately 70% of the enrolled patient population will have chronic disease (defined as initial symptom onset greater than 30 days of the procedure). At least half of the study patients will be enrolled at US sites. It is estimated that enrollment of 243 patients will take approximately 60 months.

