9.2 Sample Size Calculations

Evaluation of the primary safety hypothesis of 30-day freedom from MAE and the primary effectiveness hypothesis of 12-month primary quantitative patency requires 218 patients to determine if the performance goals have been met. Allowing for an additional 10% of patients who withdraw or are lost to follow-up, Cook intends to enroll 243 patients.

A Bayesian adaptive study was simulated to determine the sample size required to test the study hypotheses with sufficient statistical power (in the frequentist context). For the power calculations, the true quantitative patency rate following treatment with the Zilver® Vena™ Venous Stent was assumed to be 86% and the true rate of freedom from MAE at 30 days was assumed to be 97%. The results of the simulations indicate that a sample size of 218 will provide a minimum power of 0.90 with a Type I error of 0.025 for each endpoint.

It has been prespecified that patients enrolled in this study will include approximately 30% acute patients and 70% chronic patients. This patient population was defined based on the published literature describing patients treated for iliofemoral venous obstruction¹⁻³⁹ and the pattern of enrollment for the first 109 patients enrolled. Specific definitions for acute and chronic iliofemoral venous outflow obstruction are provided in Appendix B.

Full statistical details on sample size calculation are in the Statistical Analysis Plan for the study.

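### The 87% safety goal assumes a 30/70 acute/chronic mix, but the test uses the crude rate at the enrolled mix, and no rule covers a departure from 30/70

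*Combined protocol and SAP*

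**What the plan says.** Section 4.2.1 requires a performance goal "of 87% be met for 30-day freedom from MAE". That goal "is a weighted average of 85% (computed based on safety data for patients with acute disease") and "88% (computed based on safety data for patients with chronic disease"), "with the weight being prespecified as 30% acute patients and 70% chronic patients". The tested parameter is defined to "be the probability that a randomly selected patient is free from a MAE at 30 days". The decision is made "with the Binomial test for one proportion at the Type I error level of 0.025", against a one-sided alternative. This is a crude pooled proportion, with no stratification or standardisation.

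On the mix, section 8.10 says that "approximately 30% of the enrolled patient population will have acute disease". Section 9.2 bases the 30/70 split on the literature and on "the pattern of enrollment for the first 109 patients enrolled". Neither section gives a quota, a tolerance, or a rule for re-weighting the rate or recomputing the goal. Section 9.4 does not name acute versus chronic disease among its covariates or subset analyses, although its covariate list is left open. Sections 9.1 and 9.2 send the reader to a Statistical Analysis Plan for full details, and no separate SAP text is in the supplied document.

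**The concern.** The plan treats the acute/chronic mix as material for safety. Section 4.2.2 sets a single patency goal because patency was similar in the two groups. Section 4.2.1 found a three-point difference in safety and weighted for it. After that weighting, the goal stays tied to 30/70 while the tested rate follows enrolment.

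If fewer acute patients enrol, the pooled rate rises for a reason unrelated to the device, and the fixed 87% becomes an easier hurdle than the benchmarks imply. If more enrol, it becomes a harder one. Safety has a single decision rule, and section 4.2.2 makes study success depend on it.

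**Working it through.** **Inputs.** Benchmarks 0.85 and 0.88, weights 0.30 and 0.70, goal 0.87, one-sided 0.025 (section 4.2.1). N = 218 required, 243 enrolled, assumed true rate 97% (section 9.2). The acute shares below are assumed, because the realised mix is not given. I took a single final exact test. Section 9.2 mentions a simulated Bayesian adaptive study but describes no interim rule.

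**The plan's figures.** 0.30 × 85 + 0.70 × 88 = 25.5 + 61.6 = 87.1%, stated as 87%. Enrolment: 218 / (1 − 0.10) = 242.2, rounded up to 243. Both reproduce.

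**Size for the literal null.** Take the smallest r with P(X ≥ r | N, 0.87) ≤ 0.025:
- N = 218: r = 200 (91.7%), size 0.0192, power at 97% above 0.999.
- N = 243: r = 222 (91.4%), size 0.0227, power at 97% above 0.999.

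The stated Type I error is therefore met for a pooled rate of 87% or less.

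**Chance that a benchmark-equal device passes.** With acute share s, the true pooled rate is 0.85s + 0.88(1 − s). The pass probability is P(A + C ≥ r), with A ~ Bin(sN, 0.85) and C ~ Bin((1 − s)N, 0.88), stratum sizes rounded to whole patients. The matched columns use r from an exact test against the goal recomputed for that share.

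| Acute share | Matched goal | Fixed 87%, N = 218 (r = 200) | Fixed 87%, N = 243 (r = 222) | Matched, N = 218 | Matched, N = 243 |
|---|---|---|---|---|---|
| 20% | 87.4% | 0.0283 | 0.0339 | r = 201: 0.016 | r = 223: 0.021 |
| 25% | 87.25% | 0.0247 | 0.0292 | r = 200: 0.025 | r = 223: 0.018 |
| 30% | 87.1% | 0.0213 | 0.0251 | r = 200: 0.021 | r = 223: 0.015 |
| 40% | 86.8% | 0.0156 | 0.0183 | r = 200: 0.016 | r = 222: 0.018 |

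The matched goal keeps the probability at or below 0.025 in every row, with power at 97% above 0.999. At 40% it needs the same count as the fixed goal, so the low values there are no lower than an exact matched test would give.

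**How far the mix can plausibly drift.** Suppose the first 109 patients were about 30% acute (an assumption; the count is not given). Then 0.30 × 109 ≈ 33 acute patients were already enrolled and 243 − 109 = 134 remained. With no further acute patients the final share would be 33/243 = 13.6%. Reaching 20% overall needs (0.20 × 243 − 33)/134 = 15.6/134 ≈ 12% acute among the remainder. Reaching 25% needs (60.75 − 33)/134 ≈ 21%.

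**The case against.** The strongest reply is that the hypothesis in section 4.2.1 is about the pooled rate and nothing else. If the acute share is 20% and both strata sit at benchmark, the true rate is 87.4%, the null as written is false, and rejecting it is correct. A fixed, prespecified goal is a legitimate design. This stands. A reader might infer that the trial violates its stated 0.025, and the documents do not support that. The excess exists only relative to the benchmarks from which the goal was derived.

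A reader might also take an extreme mix as the likely size of the problem. At 10% acute the pass probability is 0.038 at N = 218 and 0.046 at N = 243. On the assumption above about the first 109 patients, however, a share that low could not be reached at 243 enrolled.

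Two further points limit the effect. Discreteness matters as much as modest drift: at N = 240 and 20% acute the pass probability is 0.0244, under the nominal level, and N = 243 is one of the less favourable counts. Rounding 87.1% to 87% is minor, since at 30/70 and N = 243 it leaves the pass probability at 0.0251. Finally, the SAP may already contain a rule for the mix.

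The gap that remains is that the supplied text weights the goal for mix but does not say what happens if the mix differs.

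**Conclusion.** The point holds as a modest mismatch between the goal and the tested rate. It is not a failure of the stated test. Over N = 218 and N = 243, a device no better than its benchmarks passes with probability 0.021 to 0.025 at 30% acute, 0.025 to 0.029 at 25% and 0.028 to 0.034 at 20%; at 40% the figure is 0.016 to 0.018.

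This rests on assumed acute shares, both strata exactly at 85% and 88%, a single exact final test, and no mix rule in SAP text that was not supplied. If the true rate is near the planned 97%, the decision would not change. The mismatch matters only for a device close to benchmark combined with a clear fall in the acute share.

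**What to change.** In section 4.2.1, and before outcomes are reviewed, adopt one of these:
- **Formula goal.** Define the goal as 0.85 × enrolled acute share + 0.88 × enrolled chronic share, unrounded, and apply the exact binomial test to it.
- **Standardised rate.** Test 0.30 × (acute rate) + 0.70 × (chronic rate) against 87.1%. Take the variance at the benchmark rates: 0.3² × 0.85 × 0.15 / n(acute) + 0.7² × 0.88 × 0.12 / n(chronic). Enumerating both binomials at the shares and sample sizes in the table, a z-test at 1.96 with this variance gives 0.019 to 0.025. A variance estimated from the observed rates gives 0.036 to 0.044 and should be avoided.

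Keep the fixed-87% crude test as a sensitivity analysis. If the SAP already has a rule for the mix, state it in section 4.2.1 instead.

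The cost is about one sentence. With the formula, the numeric goal is known only when enrolment closes. The required count moves by at most 1 to 2 patients (0 or 1 at the shares tabulated), and power at a true 97% stays above 0.999.

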4.2.2 Primary Effectiveness Hypothesis

The primary effectiveness endpoint is 12-month primary quantitative patency, and will be analyzed based on the intent-to-treat population. The analysis requires that the performance goal

(π_{PGE}) of 76% be met for primary quantitative patency at 12 months. The performance goal was derived based on 12-month patency data available in published literature describing patients treated with commercially available stents for acute and chronic iliofemoral venous outflow obstruction.¹⁻³⁹ Patency outcomes were similar among patients with acute and chronic disease. The effectiveness of the Zilver[®] Vena[™] Venous Stent will be established provided the null hypothesis is rejected in favor of the alternative hypothesis with the Binomial test for one proportion at the Type I error level of 0.025.

Let π_E (where E stands for effectiveness) be the probability that a randomly selected patient's treated segment is primary patent (quantitative) at 12 months, then the hypothesis is formulated as follows:

Null Hypothesis: The 12-month primary quantitative patency for patients treated with the Zilver[®] Vena[™] Venous Stent does not meet the performance goal (76%).

$$H_0: \pi_E \leq \pi_{PGE}; \text{ or } H_0: \pi_E \leq 76\%$$

Alternate Hypothesis: The 12-month primary quantitative patency for patients treated with the Zilver[®] Vena[™] Venous Stent meets the performance goal (76%).

$$H_a: \pi_E > \pi_{PGE}; \text{ or } H_a: \pi_E > 76\%$$

Study success requires that both primary hypotheses (i.e., safety and effectiveness) be met.

4.2.3 Secondary Endpoint Hypothesis

The secondary endpoint is the change from baseline in the VCSS at 1 month and at 12 months. The change from baseline in VCSS at 1 month and at 12 months will be tested against 0 for statistical significance at the Type I error level of 0.05.

Let S_{diff} be the change from baseline on VCSS at a specific time point, then the hypothesis is formulated as follows:

Null Hypothesis: The change from baseline on VCSS at a time point for patients treated with the Zilver[®] Vena[™] Venous Stent is not significantly different from 0.

$$H_0: S_{\text{diff}} = 0$$

Alternate Hypothesis: The change from baseline on VCSS at a time point for patients treated with the Zilver[®] Vena[™] Venous Stent is significantly different from 0.

$$H_a: S_{\text{diff}} \neq 0$$

Paired t-test will be used to evaluate the secondary hypotheses. In the analyses of VCSS, multiplicity will be adjusted using the Holm procedure due to the presence of multiple time points.

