8.4 Variables to be Measured to Demonstrate Achievement of Endpoints

Imaging analysis will be performed by independent core laboratories.

The clinical data and imaging measurements will be collected on standardized CRFs, which may serve as source documents. The schedule for assessments is summarized in Table 8.1.

Table 8.1. Data Collection Schedule

	Pre-Procedure	Procedure	Post-Procedure ^a	1 month	3 months	6 months	12 months	24 months	36 months	Prior to reintervention	Post reintervention
Clinical assessment including CEAP “C” classification, CIVIQ, VCSS, VDS	X			X		X	X	X	X	X	
Venography ^b		X ^c					X			X	X
2 view Stent X-ray ^c			X			X	X	X	X	X	X
Duplex Ultrasound ^d			X			X ^f	X	X ^f	X ^f	X	X
Telephone contact					X						

^aPerformed prior to hospital discharge or within 48 hours.

^bVenography must be in approximately two orthogonal views.

^cBoth obliques of the pelvis recommended.

^dDuplex ultrasound must include the treated venous segment, including cranial and caudal vessel segments.

^eVenography, ultrasound, IVUS, or CTV performed within 1 month prior to the study procedure are acceptable for the purposes of documenting in-flow tract patency. Venography, IVUS, or CTV performed within 1 month prior to the study procedure are acceptable for the purposes of documenting out-flow tract patency. Venography is required pre and post stent placement for all procedural assessments to the study vessel and treated venous segment.

^fIf patient is symptomatic and ultrasound is inadequate to assess clinical patency, venography will be performed.

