8.7.6 Follow-up Schedule

Follow-up windows are intended as guidelines only. They are not absolute and are not intended to limit data collection due to scheduling conflicts.

- *1-month clinic visit (30 days ± 5 days):* An office visit will be completed including documentation of VDS, CEAP “C” Classification, CIVIQ, and VCSS scores, and assessment of medications, hospitalizations and medical conditions.
- *3-month telephone contact (90 days ± 10 days):* Patients will be contacted by telephone by the investigative site for clinical evaluation and assessment of hospitalizations and medical conditions. Up to three attempts should be made to contact the patient.
- *6-month clinic visit (180 days ± 30 days):* An office visit will be completed including documentation of VDS, CEAP “C” Classification, CIVIQ, and VCSS scores, and assessment of medications, hospitalizations and medical conditions. Duplex ultrasound of the treated venous segment (including the cranial and caudal vessel segments) to assess clinical patency and 2 view stent x-ray (both obliques of the pelvis recommended) to assess device integrity will be performed. Confirmatory venography in approximately two orthogonal views will be performed if the patient is symptomatic and the ultrasound is inadequate to assess clinical patency.
- *12-month clinic visit (365 days ± 45 days):* An office visit will be completed including documentation of VDS, CEAP “C” Classification, CIVIQ, and VCSS scores, and assessment of medications, hospitalizations and medical conditions. Venography in approximately two orthogonal views will be performed of the treated segment and at least 1 cm cranial and caudal to the treated segment to assess quantitative patency. A calibration source (e.g., LeMaitre Ruler) will be in the field of view, but not overlapping the vessel. Duplex ultrasound of the treated venous segment (including the cranial and

caudal vessel segments) to assess clinical patency, and 2 view stent x-ray (both obliques of the pelvis recommended) to assess device integrity will be performed.

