9.5 Missing Data

Missing data will be addressed using two primary strategies: 1) multiple imputation with best available data, if appropriate, and 2) case deletion. The first strategy is multiple imputation with best available data, if appropriate. This method will be used to predict missing endpoint and imaging data. Previous clinical trial experience suggests that some portion of the imaging data may not meet the criteria for accurate review by the core laboratory; however, it is recognized that the investigator uses this information to provide the best possible care for the patient. Therefore, it is reasonable to substitute any missing core laboratory measurements with the corresponding measurements made by the investigator or institutional staff. In addition, the absence or presence of clinical sequelae may supplement the required missing core laboratory assessment of device performance. This strategy is a best approximation of the missing data value.

Statistical imputation strategies originating from Schafer⁴⁰ may also be used, supplemented with notes provided by Schafer.⁴¹ The computations (with no covariates) will be performed using PROC MI and PROC MIANALYZE in SAS version 9.3 or later, or WinBUGS 1.4 or later. Unless evidence suggests otherwise, missing at random data will be assumed.

The second strategy is case deletion. If the amount of missing data does not result in a reduction of analyzable patients to a number that is below that which is required for sufficient statistical power of the primary endpoints, then case deletion will be the method of choice for that analysis.

Additional analyses may also be performed to address missing data, including tipping point analysis.

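### At the planned loss, the 12-month VCSS paired t-test runs on completers, and scores are missing by design after reintervention, so the reported improvement would tend to be overstated

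*Combined protocol and SAP*

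**What the plan says.** Section 4.2.3 defines the endpoint: "The secondary endpoint is the change from baseline in the VCSS at 1 month and at 12 months". Each change "will be tested against 0 for statistical significance at the Type I error level of 0.05", two-sided. It adds "Paired t-test will be used to evaluate the secondary hypotheses" and "multiplicity will be adjusted using the Holm procedure due to the presence of multiple time points". Section 9.1 repeats the test and the Holm adjustment.

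VCSS is collected more often than it is tested. Table 8.1 in section 8.4 lists the clinical assessment ("classification, CIVIQ, VCSS, VDS") before the procedure, at 1, 6, 12, 24 and 36 months, and before any reintervention. Section 8.7.6 confirms the 6-month score.

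Section 9.5 covers missing data for all endpoints together:
- Multiple imputation with best available data comes first, where suitable. The statistical imputation is optional and is described as run without covariates.
- Missing at random is assumed unless evidence suggests otherwise.
- If the remaining analyzable patients are not fewer than primary-endpoint power requires, "then case deletion will be the method of choice for that analysis".
- A tipping point analysis may be added.

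Section 8.7.8 requires a VCSS before a reintervention and collects none afterwards. After bypass or amputation, participation ends at 30 days (section 8.9).

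**The concern.** A paired t-test of baseline against month 12 uses only patients with both scores. After case deletion, its mean is unbiased for the enrolled population only if a missing 12-month score is unrelated to the course of the disease.

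The protocol itself gives a reason to doubt that. A reintervention stops VCSS collection, and Appendix B defines a clinically driven reintervention by recurrent symptoms together with loss of lumen. These patients remain evaluable for the primary endpoint, because primary quantitative patency must be intervention-free. A trigger tied to primary-endpoint power therefore need not register their missing VCSS.

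The 1-month, 6-month and pre-reintervention scores carry information about the missing values, and no analysis shown uses the last two. At stake is the size of clinical improvement reported for the trial's only secondary endpoint.

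**Working it through.** **1. The plan's own figures.** Section 9.2 requires 218 patients and allows for 10% loss: 218 / 0.9 = 242.2, rounded up to 243. This reproduces the stated enrollment.

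**2. Which missing-data method applies.** At the planned loss, 243 × 0.9 = 218.7, so about 218 remain. That is not below 218, so section 9.5 selects case deletion. The margin is thin: 25 losses leave 218 and 26 leave 217.

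**3. How much VCSS could be missing at 12 months.** Loss to follow-up is 25/243 = 10.3%. Section 9.2 assumes 86% patency, so 14% fail. If every failure had a reintervention before month 12, simple addition gives 10.3% + 14% = 24.3%. This is a ceiling, because a failure first seen on the 12-month venogram still has a 12-month VCSS.

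**4. Bias by arithmetic.** Overstatement = fraction missing × (mean change in missing patients − mean change in observed patients), with improvement negative.

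| Missing patients do worse by | 10.3% missing | 24.3% missing |
|---|---|---|
| 1 point | 0.10 | 0.24 |
| 2 points | 0.21 | 0.49 |
| 3 points | 0.31 | 0.73 |
| 5 points | 0.51 | 1.21 |

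**5. Bias by simulation.** The documents give no VCSS mean, SD or correlation, so all of these inputs are assumptions.
- *Loss driven by the 6-month change; SD 4, correlation 0.6, odds of loss 2.0 to 2.7 per SD worse.* The completer mean overstates improvement by 0.15 to 0.23 points at 10% missing and 0.32 to 0.40 at 20%. At 24% with odds 2.7 it is about 0.5. A likelihood estimate using the earlier scores is biased by about 0.01 or less, and its variance is about 4 to 12% lower.
- *Same driver; true change −4, SD 4, odds 2.7, correlation 0.3 to 0.7.* Completers give −4.11 to −4.25 at 10% and −4.24 to −4.58 at 24%. A model using the 1- and 6-month scores gives −3.99 to −4.00.
- *Loss driven by the unseen 12-month score; other inputs as in the previous case.* Completers give about −4.37 at 10% and −4.83 at 24%. The model gives −4.16 to −4.32 and −4.38 to −4.72, so it removes only part of the bias.

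**6. Effect on the test against 0.**
- With SD 4 and n = 218, SE = 4/√218 = 0.27. An observed change of −3 gives |t| = 11.1. Removing 0.23 leaves 2.77/0.271 = 10.2.
- With an observed change of −4 and 10.3% missing, the missing patients would have to worsen by 4 × 0.897/0.103, about 35 points on average, to bring the overall mean to 0. The scale maximum is 10 items × 3 = 30. At 24.3% missing the figure is about 12.5 points.
- If the true change were 0 (correlation 0.5, odds 2.7, loss driven by the 6-month score), a completer test at Holm's first step of 0.05/2 = 0.025 rejects in 7.5% of simulations at 10% missing and 21.8% at 24%.

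**The case against.** **The plan does address missing data.** A reader might infer from section 4.2.3 that only patients with the visit are ever analyzed. It names a test, not a missing-data rule, and section 9.5 puts imputation first and mentions a tipping point analysis. That stands. But neither option is committed to VCSS, the computations are described as without covariates, and case deletion takes precedence at the planned loss.

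**At 20% loss the rule should leave case deletion.** 243 × 0.8 = 194, which is below 218. This holds if the missing are lost to the study. It does not hold for reintervened patients if analyzable patients are counted on the primary endpoints, since they remain evaluable for patency. If the count is instead made on VCSS, the plan moves to imputation that, as described, leaves covariates out. Section 9.5 does not settle which count applies.

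**The tested conclusion would not change.** With a substantial improvement this is right, as step 6 shows. Section 4.2.2 also rests study success on the two primary hypotheses alone.

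**A mixed model's near-zero bias is built into the simulation.** This stands too. It holds when loss depends on observed scores. Withdrawal can happen at any time (section 8.8), and a model alone does not settle how reintervention is handled.

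**The full SAP may use the 6-month score.** Section 9.1 refers to it for full detail, and that text is not in the public document. The statement here is limited to the analyses shown.

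**Conclusion.** The concern holds for the 12-month estimate. At its own planned loss the plan leads to a completer t-test, while section 8.7.8 removes 12-month scores from patients who needed further treatment. If losses follow a poor course, improvement is overstated by about 0.15 to 0.23 points at 10% missing. On an assumed true change of −3 that is 5 to 8% (0.15/3 to 0.23/3), or about 0.55 to 0.85 standard errors. At 20 to 24% missing the figure is 0.3 to 0.5 points. All VCSS inputs are assumed.

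Four stronger readings are not supported:
- Overstatement is not certain. If losses followed a good course, its sign would reverse.
- The 1-month test is little affected: few losses are expected by day 30, the 6-month score comes later, and no 1-month bias has been shown.
- VCSS is not the only clinical outcome formally tested. The primary safety endpoint tests freedom from related death, symptomatic pulmonary embolism and clinically driven reintervention, among other events.
- A repeated-measures model does not remove all bias. At 10% missing, 0.16 to 0.32 points remain if loss depends on the unseen 12-month score.

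**What to change.** In sections 4.2.3 and 9.1:
- Make the main 12-month VCSS analysis a mixed model for repeated measures on all available scores at baseline, 1, 6 and 12 months, with visit as a factor and unstructured covariance. Test the 1- and 12-month changes from this model with the same Holm procedure. Keep the paired t-tests as sensitivity analyses.
- For patients with a reintervention before 12 months, use the pre-reintervention VCSS already collected, entered as the 12-month value, and state that the endpoint then describes the outcome before further treatment.

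In section 9.5, state that this approach governs VCSS in place of the general case-deletion rule, and make the tipping point analysis of 12-month VCSS mandatory.

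The cost is wording, one standard model and one sensitivity analysis. No new patients, visits or data are needed. The reported improvement may be smaller, and the 1-month test gains little.
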